### C.11.4 Continuous Data: Bayesian version of a t-test.

Assuming that the quantity of interest Y follows a  $N(\mu, \sigma^2)$  distribution, and placing a uniform prior distribution on  $(\mu, \log(\sigma))$ , the posterior distribution of  $\mu$  has the form^27

$$\left[ \frac{\mu - \bar{y}}{s/\sqrt{n}} \mid Y \right] \sim t_{n-1}$$

Employing this for both  $\mu_t$  and  $\mu_c$ , the distribution of  $(\mu_t - \mu_c)$  can be estimated in Monte Carlo fashion by drawing a large number of observations (eg, 25000) from a  $t_{n-1}$  distribution for  $n = n_t$  and  $n = n_c$ , back-transforming these observations to the  $\mu_t$  and  $\mu_c$ -scales, and subtracting. The posterior probability  $P(\mu_t - \mu_c > \delta \mid \text{data})$  is estimated as the proportion of observed values of  $(\mu_t - \mu_c)$  that exceed  $\delta$ . A 95% equal-tail Bayesian credible interval can be calculated from the 2.5th and 97.5th percentiles of the sampled distribution of  $\mu_t - \mu_c$ . Credible intervals for  $\mu_t$  and  $\mu_c$  can be individually calculated as the 2.5th and 97.5th percentiles from their respective (scaled  $t$ ) posterior distributions.

#### C.11.5 Continuous Data (Distribution-free, Superiority): Bayesian Version of a Wilcoxon Rank-Sum Test

For this test, data are ranked. Analogous to the Wilcoxon Rank-Sum test, observations in each group are replaced by their ranks in the combined order statistic. Then the two groups of rank-transformed data are compared via the Bayesian version of a t-test, above. It has been shown that conducting a two-sample t-test on rank-transformed data is approximately equivalent to the Wilcoxon Rank-Sum test.

Non-inferiority can be evaluated by first subtracting a margin ( $\delta$ ) from each observation in one treatment group prior to the rank transformation.

### C.12 Multiplicity Considerations

It is recognized that with a multiplicity of tests comes an inflation in the chance of a false finding of superiority or non-inferiority. Therefore, for the purpose of seeking approved labeling claims on designated secondary objectives, the following standard will be used: If the primary objective demonstrates non-inferiority, claims will be sought for selected secondary non-inferiority and superiority objectives and for superiority on the primary objective metric. These will be tested via a hierarchical (sequential) testing order that preserves the overall study-wise type I error rate at the level of 0.05, while requiring all non-inferiority tests to meet a nominal type I error rate of 0.05 and all superiority tests to meet a nominal type I error rate of 0.025. The testing order is specified below. The following objectives are tested in order, and testing continues if and only if all previous objectives have met their designated success criterion.

1. Primary endpoint (non-inferiority)
2. Transvalvular mean gradient at 12 months (non-inferiority)
3. Effective orifice area at 12 months (non-inferiority)
4. Change in NYHA classification from baseline to 12 months (non-inferiority)
5. Change in KCCQ score from baseline to 30 days (non-inferiority)

All of the above are non-inferiority tests and are tested with a type I error standard of 0.05. If all of the above tests meet their success criterion, the type I error rate of 0.05 that is passed on from the above tests will be split equally (using a Bonferroni justification) between the following parallel subfamilies, so that each subfamily is tested using a type I error rate of 0.025:

---

10 Berry D & Lindgren B, *Statistics: Theory and Methods*, 2ed. Belmont, CA: Duxbury, 1996, p 505.

11 Conover WJ & Iman RL, "Rank transformations as a bridge between parametric and nonparametric statistics," *American Statistician* 35 (1981), 124-129.

Subfamily #1: Primary endpoint (superiority)

Subfamily #2: Secondary (superiority) objectives #5–#18 as enumerated below, tested in ordered sequence such that all  $\alpha$  is passed on to subsequent tests if a test criterion is met, while all testing stops if a test criterion is not met. This procedure controls the type I error rate of this subfamily at the level 0.025.

It is not necessary to “pass” all objectives in one subfamily in order to test the objective(s) in the other subfamily.

Since, for all secondary objectives, the prior distributions are flat or nearly flat, virtually all information in the model is contained within the likelihood. Therefore, a rule that determines  $P(H | \text{data}) > \theta$  must induce a “critical value” in the data space that is approximately equal to the critical value defined by a  $(1-\theta)$ -level significance test in the setting of a standard frequentist hypothesis test, and the type 1 error of each secondary objective analysis must therefore approximate the quantity  $1 - \theta$ . This is consistent with the statement of Gelman et al. that “[i]n various simple one-sided hypothesis tests, conventional p-values may correspond with posterior probabilities, under noninformative prior distributions” and the statement of Albert that “a Bayesian probability of a hypothesis is equal to the p-value for one-sided testing problems when a vague prior distribution is placed on the parameter”. It follows that frequentist methods that control type 1 errors among multiple objectives must apply, at least approximately, to posterior probabilities in an analogous fashion.

For the purposes of seeking claims, these objectives will only be evaluated once, at the same time as non-inferiority of the primary objective is established. The only exception to this is the primary endpoint superiority test, which carries the possibility of a delayed determination of superiority (as described in Section 4.2.1 and Appendix G.5 of this SAP document) and may thus meet its success criterion at a different time.

The remaining secondary objectives may be of interest for scientific or financial reasons but will not be the basis for supporting labeling claims; they are thus outside of the hierarchical testing procedure. Similarly, for those objectives that test non-inferiority, if non-inferiority is established, a test of superiority will also be conducted, but unless specifically itemized in the list, such superiority testing is not part of the hierarchical testing procedure; these superiority tests may be of interest for scientific or financial reasons but will not be the basis for supporting labeling claims.

### C.12.1 Ordered List of Secondary Objectives to be Tested To Support Labeling Claims

1. Transvalvular mean gradient at 12 months (non-inferiority): TAVI vs. SAVR (secondary objective #12). The hypothesis of interest is

$$H: \mu_{\text{TAVI}} < \mu_{\text{SAVR}} + 5$$

where  $\mu_{\text{TAVI}}$  and  $\mu_{\text{SAVR}}$  denote the average mean gradient at 12 months, measured in mmHg. This objective will be evaluated using a Bayesian version of a two-sample t-test (see Section C.11). The posterior probability  $P(H | \text{data})$  will be calculated and compared to a threshold of 0.95.

**Rationale for Delta:** A difference less than 5 mmHg for mean gradient is not considered clinically relevant for the SURTAVI Steering Committee.

 Albert J, *Bayesian Computation with R*, 1st ed. New York: Springer, 2007.

2. Effective orifice area at 12 months (non-inferiority): TAVI vs. SAVR (secondary objective #12). The hypothesis of interest is

$$H: \mu_{TAVI} > \mu_{SAVR} - 0.1$$

where  $\mu_{TAVI}$  and  $\mu_{SAVR}$  denote the mean effective orifice area at 12 months, measured in  $\text{cm}^2$ . This objective will be evaluated using a Bayesian version of a two-sample t-test (see Section C.11). The posterior probability  $P(H | \text{data})$  will be calculated and compared to a threshold of 0.95.

**Rationale for Delta:** A difference less than 0.1  $\text{cm}^2$  for effective orifice area is not considered clinically relevant for the SURTAVI Steering Committee.

3. Change in NYHA classification from baseline to 12 months (non-inferiority): TAVI vs. SAVR (secondary objective #8). The hypothesis of interest is

$$H: \mu_{TAVI} > \mu_{SAVR} - 0.375$$

where  $\mu_{TAVI}$  and  $\mu_{SAVR}$  denote the mean number of classification improvements in NYHA from baseline to 12 months. For subjects with NYHA categories at both baseline and 12 month visit, the NYHA classification improvements will be calculated as  $\text{NYHA}_{\text{baseline}} - \text{NYHA}_{12\text{month}}$ . The objective will be evaluated using a Bayesian version of a two-sample t-test (see Section C.11). The posterior probability  $P(H | \text{data})$  will be calculated and compared to a threshold of 0.95.

**Rationale for Delta:** A difference less than 0.375 for NYHA classification is not considered clinically relevant for the SURTAVI Steering Committee.

4. Change in Kansas City Cardiomyopathy Questionnaire (KCCQ) score from baseline to 30 days (non-inferiority): TAVI vs. SAVR (secondary objective #11). The hypothesis of interest is

$$H: \mu_{TAVI} > \mu_{SAVR} - 5$$

where  $\mu_{TAVI}$  and  $\mu_{SAVR}$  denote the mean improvements in the KCCQ score from baseline to 30 days. For subjects with KCCQ score at both baseline and 30 days, the improvement in KCCQ will be calculated as  $\text{KCCQ}_{30\text{day}} - \text{KCCQ}_{\text{baseline}}$ . The objective will be evaluated using a Bayesian version of a two-sample t-test (see Section C.11). The posterior probability  $P(H | \text{data})$  will be calculated and compared to a threshold of 0.95.

**Rationale for Delta:** A 5 point improvement or decrease in KCCQ is the minimum difference that is clinically relevant. (Spertus J, et al, "Monitoring clinical changes in patients with heart failure: A comparison of methods," American Heart Journal 2005;150:710-715.)

5. Length of index procedure hospital stay after TAVI vs. SAVR (secondary objective #18). The hypothesis of interest is

$$H: \mu_{TAVI} < \mu_{SAVR}$$

where  $\mu_{TAVI}$  and  $\mu_{SAVR}$  denote the mean length of index hospital stay. The objective will be evaluated using a Bayesian version of a two-sample t-test (see Section C.11). The posterior probability  $P(H | \text{data})$  will be calculated and compared to a threshold of 0.975.

6. Transvalvular mean gradient at 12 months (superiority): TAVI vs. SAVR (secondary objective #12). The hypothesis of interest is

$$H: \mu_{TAVI} < \mu_{SAVR}$$

where  $\mu_{TAVI}$  and  $\mu_{SAVR}$  denote the average mean gradient at 12 months, measured in mmHg. This objective will be evaluated using a Bayesian version of a two-sample t-test (see Section C.11). The posterior probability  $P(H | \text{data})$  will be calculated and compared to a threshold of 0.975.

7. Effective orifice area at 12 months (superiority): TAVI vs. SAVR (secondary objective #12). The hypothesis of interest is

$$H: \mu_{TAVI} > \mu_{SAVR}$$

where  $\mu_{TAVI}$  and  $\mu_{SAVR}$  denote the mean effective orifice area at 12 months, measured in  $\text{cm}^2$ . This objective will be evaluated using a Bayesian version of a two-sample t-test (see Section C.11). The posterior probability  $P(H | \text{data})$  will be calculated and compared to a threshold of 0.975.

8. Change in Kansas City Cardiomyopathy Questionnaire (KCCQ) score from baseline to 30 days (superiority): TAVI vs. SAVR (secondary objective #11). The hypothesis of interest is

$$H: \mu_{TAVI} > \mu_{SAVR}$$

where  $\mu_{TAVI}$  and  $\mu_{SAVR}$  denote the mean improvements in the KCCQ score from baseline to 30 days. For subjects with KCCQ score at both baseline and 30 days, the improvement in KCCQ will be calculated as  $KCCQ_{30\text{day}} - KCCQ_{\text{baseline}}$ . The objective will be evaluated using a Bayesian version of a two-sample t-test (see Section C.11). The posterior probability  $P(H | \text{data})$  will be calculated and compared to a threshold of 0.975.

9. Days alive out of the hospital at 12 months after TAVI vs. SAVR (secondary objective #10). The hypothesis of interest is

$$H: \mu_{TAVI} > \mu_{SAVR}$$

where  $\mu_{TAVI}$  and  $\mu_{SAVR}$  denote the mean number of days alive out of the hospital at 12 months. The objective will be evaluated using a Bayesian version of a two-sample t-test (see Section C.11). The posterior probability  $P(H | \text{data})$  will be calculated and compared to a threshold of 0.975.

10. Days alive out of the hospital at 24 months after TAVI vs. SAVR (secondary objective #10). The hypothesis of interest is

$$H: \mu_{TAVI} > \mu_{SAVR}$$

where  $\mu_{TAVI}$  and  $\mu_{SAVR}$  denote the mean number of days alive out of the hospital at 24 months. The objective will be evaluated using a Bayesian version of a two-sample t-test (see Section C.11). The posterior probability  $P(H | \text{data})$  will be calculated and compared to a threshold of 0.975.

11. Change in SF-36 Physical Summary Scale from baseline to 3 months: TAVI vs. SAVR (secondary objective #11). The hypothesis of interest is

$$H: \mu_{TAVI} > \mu_{SAVR}$$

where  $\mu_{TAVI}$  and  $\mu_{SAVR}$  denote the mean improvements in the SF-36 Physical Summary Scale from baseline to 3 months. The objective will be evaluated using a Bayesian version of a two-sample t-test (see Section C.11). The posterior probability  $P(H | \text{data})$  will be calculated and compared to a threshold of 0.975.

12. Change in EQ-5D from baseline to 3 months: TAVI vs. SAVR (secondary objective #11). The hypothesis of interest is

$$H: \mu_{TAVI} > \mu_{SAVR}$$

where  $\mu_{TAVI}$  and  $\mu_{SAVR}$  denote the mean improvements in the EQ-5D from baseline to 3 months. The objective will be evaluated using a Bayesian version of a two-sample t-test (see Section C.11). The posterior probability  $P(H | \text{data})$  will be calculated and compared to a threshold of 0.975.

13. Incidence of MACCE at 30 days or hospital discharge, whichever is longer: TAVI vs. SAVR (secondary objective #1). The hypothesis of interest is

$$H: \pi_{TAVI} < \pi_{SAVR}$$

where  $\pi_{TAVI}$  and  $\pi_{SAVR}$  denote the binary rate of MACCE at 30 days or hospital discharge (if longer). The posterior probability  $P(H | \text{data})$  will be calculated and compared to a threshold

of 0.975. The statistical method will be the Bayesian version of a comparison of proportions (see Section C.11).

14. Incidence of major vascular complication at 30 days or hospital discharge, whichever is longer: TAVI vs. SAVR (secondary objective #3). The hypothesis of interest is

$$H: \pi_{TAVI} < \pi_{SAVR}$$

where  $\pi_{TAVI}$  and  $\pi_{SAVR}$  denote the binary rate of major vascular complications at 30 days or hospital discharge (if longer). The posterior probability  $P(H | \text{data})$  will be calculated and compared to a threshold of 0.975. The statistical method will be the Bayesian version of a comparison of proportions (see Section C.11).

15. Incidence of major or life-threatening bleeding events at 30 days or hospital discharge, whichever is longer: TAVI vs. SAVR (secondary objective #3). The hypothesis of interest is

$$H: \pi_{TAVI} < \pi_{SAVR}$$

where  $\pi_{TAVI}$  and  $\pi_{SAVR}$  denote the binary rate of major or life-threatening bleeding events at 30 days or hospital discharge (if longer). The posterior probability  $P(H | \text{data})$  will be calculated and compared to a threshold of 0.975. The statistical method will be the Bayesian version of a comparison of proportions (see Section C.11).

16. Incidence of all strokes at 30 days or hospital discharge, whichever is longer: TAVI vs. SAVR (secondary objective #15). The hypothesis of interest is

$$H: \pi_{TAVI} < \pi_{SAVR}$$

where  $\pi_{TAVI}$  and  $\pi_{SAVR}$  denote the binary rate of all strokes at 30 days or hospital discharge (if longer). The posterior probability  $P(H | \text{data})$  will be calculated and compared to a threshold of 0.975. The statistical method will be the Bayesian version of a comparison of proportions (see Section C.11).

17. Incidence of moderate/severe aortic insufficiency after TAVI vs. SAVR (secondary objective #12). The hypothesis of interest is

$$H: \pi_{TAVI} < \pi_{SAVR}$$

where  $\pi_{TAVI}$  and  $\pi_{SAVR}$  denote the proportion of subjects with moderate/severe aortic insufficiency at the discharge echo. The posterior probability  $P(H | \text{data})$  will be calculated and compared to a threshold of 0.975. The statistical method will be the Bayesian version of a comparison of proportions (see Section C.11).

18. New pacemaker implant rate for TAVI at 30 days or hospital discharge, whichever is longer (secondary objective #7). The hypothesis of interest is

$$H: \pi_{TAVI} < 30\%$$

where  $\pi_{TAVI}$  denote the binary rate of new pacemaker implants for TAVI at 30 days or hospital discharge (if longer). The posterior probability  $P(H | \text{data})$  will be calculated and compared to a threshold of 0.975. The statistical method will be the Bayesian version of a comparison of proportions (see Section C.11).

Other than the hierarchical testing procedure described above, no further multiplicity adjustments will be made in the analyses of the secondary endpoints. Summary data from other secondary objectives, such as device success and procedural success from secondary objectives #20 and #21, respectively, may be provided in the device labeling. However, no claims of statistical significance or other statistical inference will be made.

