**C.4.2 Randomization, Sample Size, and Analysis Plan**

Randomization will follow a 1:1 (treatment:control) allocation ratio and be stratified by site and need for revascularization, using a blocked randomization scheme with blocks of randomly varying sizes. The sample size for the mITT population is 1600 subjects.

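### Five change-from-baseline claim tests (NYHA, KCCQ, SF-36, EQ-5D) use an unadjusted t-test and give up precision that the collected baseline value would supply, mainly at the cost of superiority objectives 8, 11 and 12

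*Combined protocol and SAP*

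**What the plan says.** All references are to SAP version 6.0 unless stated.

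- **NYHA, objective 3 (non-inferiority, margin 0.375 classes).** "For subjects with NYHA categories at both baseline and 12 month visit, the NYHA classification improvements will be calculated as" baseline minus 12 months.
- **KCCQ, objectives 4 (non-inferiority, margin 5 points) and 8 (superiority).** "For subjects with KCCQ score at both baseline and 30 days, the improvement in KCCQ will be calculated as" 30 days minus baseline.
- **SF-36, objective 11 (superiority).** The means compared "denote the mean improvements in the SF-36 Physical Summary Scale from baseline to 3 months". Objective 12 does the same for EQ-5D. Neither prints the subtraction, but mean improvement from baseline amounts to the same quantity.
- **Method.** All five go to C.11.4, headed "Continuous Data: Bayesian version of a t-test". Each arm's posterior there depends only on that arm's mean, SD and n.
- **Baseline data.** C.14.4 has all three questionnaires completed at baseline, before the subject learns the allocation. Objective 3 itself requires baseline NYHA.
- **Testing order (C.12).** Objectives 3 and 4 are gatekeepers, tested at 0.05. Superiority objectives 5 to 18 form Subfamily #2, tested in fixed sequence at 0.025 and stopping at the first miss. Superiority on the primary endpoint is a separate, parallel Subfamily #1. The secondary claims are evaluated once only.
- **Randomisation (C.4.2).** Allocation is 1:1, to "be stratified by site and need for revascularization".

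No adjusted version of these five tests is planned. The sensitivity analyses in C.8 concern the primary objective. C.13 and C.14.1 examine heterogeneity and subgroups and do not adjust these tests.

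**The concern.** Subtracting the baseline fixes its coefficient at 1. When follow-up depends on baseline less steeply than that, the subtraction adds noise that a fitted coefficient would remove. The information needed is already in the database.

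What is at stake is power for labelling claims that get a single look. A miss on objective 8 removes ten later claims (9 to 18), a miss on 11 removes seven (12 to 18), and a miss on 12 removes six (13 to 18). The last six include MACCE, bleeding and stroke. Objective 11 is the most exposed: protocol Appendix R.12.2.1 limits the 3-month SF-36 to five countries, so it has fewer subjects. The SAP states no power for any of these tests.

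**Working it through.** **Inputs from the documents.** 1600 mITT subjects randomised 1:1 (C.4.2), so at most 800 per arm; thresholds 0.95 (objectives 3, 4) and 0.975 (8, 11, 12); margins 5 points and 0.375 classes.

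**The plan's own figure.** There is none for these tests. The only sample-size calculation is for the primary endpoint (C.4.2.1), and it reproduces: the Farrington-Manning method with rates 0.17/0.17, margin 0.07, one-sided alpha 0.05 and power 95% gives 628.6 per arm, 1258 in total; 1258/0.94 = 1338.3, so 1339; 1339/0.875 = 1530.3, so 1531.

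**Assumed.** The baseline/follow-up correlation r, the SDs, and the number with paired data. The documents give none of these.

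**Step 1: variance per subject.** Let the baseline SD be 1 and the follow-up SD be k.

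- Change score: 1 + k² − 2rk
- Adjusted for baseline: k²(1 − r²)
- Difference: (1 − rk)²

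Since rk is the slope of follow-up on baseline, the loss is zero only when that slope is 1.

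**Step 2: equal SDs (k = 1).** The ratio of adjusted to change-score variance is (1 − r²)/[2(1 − r)] = (1 + r)/2.

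| r | Change | Adjusted | Ratio |
|---|---|---|---|
| 0.3 | 1.40 | 0.91 | 0.65 |
| 0.5 | 1.00 | 0.75 | 0.75 |
| 0.7 | 0.60 | 0.51 | 0.85 |

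The same precision then needs 35%, 25% or 15% fewer subjects.

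**Step 3: unequal SDs, k from 0.8 to 1.25, r from 0.3 to 0.7.**

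- Lowest ratio, k = 0.8 and r = 0.3: 0.5824/1.16 = 0.50
- Highest ratio, k = 1.25 and r = 0.7: 0.7969/0.8125 = 0.98 (slope 0.875)

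**Step 4: power for superiority.** A test with 80% power on the change score at one-sided 0.025 has a standardised effect of 1.960 + 0.842 = 2.802. Dividing by the square root of the ratio gives 3.475, 3.235 and 3.039. Subtracting 1.960 gives power of 93.5%, 89.9% and 86.0% at r = 0.3, 0.5 and 0.7.

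A simulation (600 per arm, true difference 0.15 SD, an assumed 20% in a revascularisation stratum with a 0.3 SD effect, 4000 trials) compared the change-score t-test with a model containing baseline and stratum. Power was 0.60 against 0.79, 0.73 against 0.85, and 0.91 against 0.95. Type I error was 0.021 to 0.029 for both methods, consistent with 0.025.

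**Step 5: the gatekeepers.**

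- KCCQ, least favourable case examined (SD 25, 600 per arm, r = 0.3): change SD 25 × √1.4 = 29.6, SE 29.6 × √(2/600) = 1.71, 5/1.71 − 1.645 = 1.28, power 0.90. Adjusted: 0.98. The other cases (SD 20 or 25, 600 to 800 per arm, r up to 0.7) are higher.
- NYHA (SD 0.6 to 0.8, r 0.2 to 0.5, 600 per arm): power above 0.99999 on the change score.

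For KCCQ superiority with an assumed true difference of 3 points, the same KCCQ grid gives 0.42 to 0.97 on the change score and 0.59 to 0.99 after adjustment.

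**The case against.** The strongest reply is that this costs only efficiency. **That stands.** The change-score t-test is unbiased in a randomised comparison and controls type I error, so no claim can be falsely won because of it. The size of the gain is also unknown, and could be as small as 2% of variance (step 3).

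A reader might go further in four ways that the documents do not support.

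- **That chance baseline imbalance is a second harm.** With slope b, an imbalance d enters the change score as (b − 1)d. It enters in full only if b = 0, averages to zero over randomisations, and is already counted in the variances above.
- **That the gatekeepers are in danger.** Under the assumed SDs the NYHA test has power near 1 and the KCCQ test 0.90 or more as planned.
- **That a miss on 8, 11 or 12 stops everything.** C.12 says that one subfamily need not pass for the other to be tested, so primary superiority is unaffected.
- **That the primary analysis should be stratified too.** The thresholds 0.971 and 0.989 were set by simulating the unstratified analysis (C.4.2.2). The gain would be small: with an assumed 20% needing revascularisation and event rates of 25% and 15%, the between-stratum variance is 0.2 × 0.8 × 0.10² = 0.0016 against 0.17 × 0.83 = 0.141, about 1.1%. Nor is the stratum ignored, since C.13 tests its interaction with treatment and C.14.1 makes it a subgroup.

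One technical objection also stands: C.11.4 lets each arm have its own variance, and a standard linear model would not. The replacement should keep that feature.

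**Conclusion.** The point holds as a loss of precision in five claim tests, not as bias or an inflated error rate. Under equal SDs and r of 0.3 to 0.7, the unadjusted analysis needs 1/0.85 = 1.18 to 1/0.65 = 1.54 times as many subjects for the same precision. Allowing unequal SDs, the variance ratio runs from about 0.50 to 0.98. These figures rest entirely on assumed correlations and SDs.

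The practical consequence falls on superiority objectives 8, 11 and 12, and through them on the remainder of Subfamily #2. The change is worth making because the sequence is tested once and the baseline data are already collected.

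**What to change.** Amend C.11.4 and C.12.1 before comparative data on these endpoints are seen.

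- For objectives 3, 4, 8, 11 and 12, fit a normal linear model with flat priors: follow-up value on treatment and baseline value. Need for revascularisation may be added as a covariate.
- Allow a separate residual variance in each arm, as C.11.4 does now.
- Base P(H | data) on the treatment coefficient, signed so that improvement is positive (for NYHA, reverse the sign). With baseline in the model, this coefficient is the same whether the outcome is the follow-up value or the change, so the margins (0.375 and 5) and thresholds (0.95 and 0.975) carry over.
- Leave the primary decision analysis unchanged. Any revascularisation-stratified version of it should be labelled supportive.

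The cost is SAP wording and a modest change to the analysis program. No new data are needed, and the subjects analysed stay the same, because a change score already requires both values.

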#### C.4.2.2 Analysis Plan

The sample size look analysis (timed when 1400 subjects had entered the mITT population) occurred prior to the change of margin; the conclusion of this analysis was that 1400 would be inadequate to establish non-inferiority (using  $\delta = 0.05$ ) and that subject accrual should continue (refer to Appendix G.1 for sample size determination algorithm). With the re-design accompanying the change of margin, an interim analysis (timed to occur when 1400 mITT subjects have reached 12 months) for the purpose of declaring an early win will occur and all enrolled mITT subjects will be included in the analysis. At this analysis, if  $P(H_{\delta=0.07} | \text{data}) > \Psi$ , non-inferiority will be declared at this time, and a regulatory submission will follow. On the other hand, if  $P(H_{\delta=0.07} | \text{data}) \leq \Psi$ , all mITT subjects will be followed to 24 months, when a final analysis will occur. At the final analysis, the standard for trial success will again be  $P(H_{\delta=0.07} | \text{data}) > \Psi$ . These two analyses are termed “Win Looks”.

If, at the early interim “Win Look,” non-inferiority is established, a test of superiority will immediately follow. If  $P(H_{\delta=0} | \text{data}) > \Psi_{\text{SUP}}$ , superiority will be established at this time. However, if  $P(H_{\delta=0} | \text{data}) \leq \Psi_{\text{SUP}}$ , subjects will continue to be followed and analyzed according to the same analysis plan (i.e., with one more possible “Win” analysis when all mITT subjects have reached 24 months). At the final “Win” analysis, if  $P(H_{\delta=0} | \text{data}) > \Psi_{\text{SUP}}$ , a delayed determination of superiority will be made.

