### C.7.3.1 Subject Follow-up for 'Early Win' Analysis

The Early Win analysis occurs when 1400 mITT subject have reached 12 months, assuming that accrual did not stop for futility. Thus it is expected that approximately 1400 subjects will have 12 month follow-up at this analysis, except for perhaps 3% lost-to-follow-up during this 12 months, and perhaps a little variability due to the follow-up visit window. The number of subjects who have reached 24 months as of this analysis varies primarily with accrual rate. The table below displays the probable counts of 24-month observations at the early win analysis .

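### Objective 10, the only 24-month secondary objective in the labeling sequence, is tested once, most likely at the Early Win look before its follow-up is complete, and a miss bars claims on objectives 11–18

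*Combined protocol and SAP*

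**What the plan says.** References are to SAP version 6.0 (CIP version 12.0).

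- **Sequence.** Under C.12, once the primary endpoint and four secondary objectives have shown non-inferiority, testing splits into two parallel subfamilies at 0.025 each. Subfamily #1 is primary superiority. Subfamily #2 takes secondary objectives 5–18 in fixed order, "while all testing stops if a test criterion is not met". C.12 requires "all superiority tests to meet a nominal type I error rate of 0.025".
- **Timing.** For claims, "these objectives will only be evaluated once, at the same time as non-inferiority of the primary objective is established". C.12 adds: "The only exception to this is the primary endpoint superiority test, which carries the possibility of a delayed determination of superiority".
- **The objective.** Entry 10 in C.12.1 is "Days alive out of the hospital at 24 months after TAVI vs. SAVR (secondary objective #10", a Bayesian two-sample t-test against 0.975. Entries 11 and 12 are 3-month SF-36 and EQ-5D. Entries 13–16 and 18 are event rates at 30 days or discharge. Entry 17 is aortic insufficiency on the discharge echo.
- **The look.** C.4.2.2 places the Early Win analysis as "timed to occur when 1400 mITT subjects have reached 12 months". From C.4.2, "The sample size for the mITT population is 1600 subjects". C.7.3.1 says "The number of subjects who have reached 24 months as of this analysis varies primarily with accrual rate", and Table 6 gives 808 (expected), 978 (slow) and 639 (fast).
- **Partial follow-up.** C.11.3 provides predictions for dichotomous endpoints. The t-test in C.11.4 has none. Secondary endpoint 10 in C.10 defines a ratio whose denominator runs to the last follow-up date, then adds a comparison of day counts at 12 and 24 months. It does not say how a subject short of 24 months enters the 24-month count.

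**The concern.** A fixed sequence works best when each gate has mature data on the day it is tested. The other 17 secondary objectives are measured at 12 months or earlier, which suits a look timed on 12-month follow-up. Objective 10 is the exception. It sits ahead of eight objectives measured at 3 months or earlier, has one attempt, and has neither the prediction step nor the delayed test that the 24-month primary endpoint receives.

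At stake is the sponsor's ability to claim any of objectives 11–18. They could lose claim eligibility because an endpoint unrelated to their own maturity was tested before its follow-up was in.

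**Working it through.** **1. Reproduce Table 6.** The look falls 12 months after the 1400th subject enters. Subjects past 24 months are those who entered at least 12 months before that subject: 1400 − 12r, where r is the monthly accrual from month 22 (C.7.3). The shortcut is valid because the first 21 months sum to 576, below every result here. Multiply by 0.94 for the 6% dropout in C.7.1.

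| Accrual | r | 1400 − 12r | × 0.94 | Table 6 | Share of 1600 |
|---|---|---|---|---|---|
| Expected | 45 | 860 | 808.4 | 808 | 50.5% |
| Slow | 30 | 1040 | 977.6 | 978 | 61.1% |
| Fast | 60 | 680 | 639.2 | 639 | 39.9% |

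All three reproduce. Table 7, which averages over trials that stop at 1400 or 1600, gives 50.4%–56.8% under expected accrual and 39.9%–69.3% over all scenarios.

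**2. Maturity of objectives 11–18.** Subject 1600 enters 200/r months after subject 1400, so has 12 − 200/r months of follow-up at the look: 7.6 (expected), 5.3 (slow), 8.7 (fast). Every subject is past the 3-month, 30-day and discharge assessments. Ordinary missing data remain, and Appendix R.12.2 limits the 3-month SF-36 to five countries.

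**3. How likely is this look?** Table 3, rate 0.17 and difference 0: early wins 0.8896, all wins 0.9402. The ratio is 94.6%. Table 3 includes trials that stop at 1400 for promise (0.4146), whereas this trial continued. Even if all of those won early, the continuing trials contribute at least 0.8896 − 0.4146 = 0.4750 early wins against at most 0.0506 late ones, so the early share is at least 0.4750/0.5256 = 90.4%.

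**4. Illustrative power.** The documents give no SD or effect for days alive out of hospital, so the full-data power P is an assumption. Completers at full follow-up: 1600 × 0.94 = 1504. With one-sided 0.025 and n subjects at the look,

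power = Φ[(1.960 + z_P) × √(n/1504) − 1.960].

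For P = 80% and n = 808: 2.802 × 0.733 = 2.054, and Φ(0.094) = 53.7%.

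| Assumed power on 1504 | Expected, 808 | Slow, 978 | Fast, 639 |
|---|---|---|---|
| 80% | 53.7% | 61.7% | 44.7% |
| 90% | 66.2% | 74.3% | 56.1% |
| 95% | 75.3% | 82.8% | 65.2% |
| 99% | 88.2% | 93.3% | 79.8% |

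Under expected accrual the loss is about 26, 24, 20 and 11 points.

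**5. The other reading of the day count.** Suppose subjects short of 24 months enter with their days to last follow-up. Ignoring deaths and dropout, 860 subjects contribute 24 months, 540 average 18, and 200 average (12 + 7.56)/2 = 9.78. That is (860 × 24 + 540 × 18 + 200 × 9.78)/(1600 × 24) = 84% of the full person-time. The variable would then no longer be a 24-month count.

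**The case against.** A fixed sequence may follow the sponsor's priorities, and the stated order controls type I error. The loss is conservative, falls only on the sponsor's claims, and arises only if objectives 1–9 pass and non-inferiority is declared early. All of that stands. It limits the seriousness of the point but does not remove it.

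Several stronger readings are tempting, and the documents do not support them:

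- **That the test certainly runs on half the sample.** Table 6 counts subjects with a 24-month outcome. The entries for objectives 3, 4 and 8 restrict analysis to subjects with both measurements. The entry for objective 10 has no such restriction. The supportable statement is that the rule is missing.
- **That the sample would be enriched for deaths.** This would follow only if late enrollees who died were counted and those still alive were not. No section says so, and with equal mortality both arms would be affected alike.
- **That the chance of reaching objectives 11–18 falls by a fixed 25 points.** That figure belongs to objective 10 alone at an assumed 80–90% power. Reaching objective 11 also requires the primary and objectives 1–9, including the related 12-month day count.
- **That objectives 11–18 would go unanalyzed.** The sequence governs labeling claims. The secondary comparisons in C.10 are still reported.

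**Conclusion.** The concern holds as a weakness in claim strategy. Objective 10 is the only 24-month endpoint among the 18 listed secondary objectives. It is evaluated once, most likely at a look where about 808 subjects have 24-month outcomes, with no prediction step and no stated rule for the rest. A miss makes eight objectives with completed visits ineligible for labeling claims.

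The size of the effect is not known from the documents. On the completers reading with expected accrual, the illustrative loss in objective 10's power is 11 to 26 points for assumed full-data power between 99% and 80%. It is larger with fast accrual, smaller with slow accrual, and conditional on an Early Win with objectives 1–9 passed. After a late win the 24-month data are as complete as they will be and the problem disappears. A reader might also infer inflated type I error, but there is none: the primary analysis and primary superiority are untouched.

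**What to change.** Move objective 10 to the end of Subfamily #2. Evaluate it once, when all mITT subjects have reached 24 months, and only if objectives 5–9 and 11–18 have passed. Name it beside primary superiority in the C.12 exception to single-time evaluation. Leave the order and timing of the other objectives unchanged.

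This costs no alpha: the objective is last, is tested once, and passes nothing on, so the subfamily stays at 0.025. The SAP already allows a delayed test for primary superiority, and follow-up to 24 months and beyond is already planned.

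The real costs are these:

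- The 24-month claim comes later than the rest of the package and now depends on objectives 11–18 passing. The 12-month version, objective 9, keeps its place.
- The 1400-subject sample-size look has already taken place (C.4.2.2). The SAP should record that the change follows that look and rests on follow-up timing, not on outcome data.
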